3. General Description of Study Design

Retrospective part

Patient characteristics and disease-related (trigger finger) variables will be collected retrospectively from patient charts on EPIC.

Prospective part

This will be a prospective two-arm study. Patients will either be treated with ultrasound-guided trigger finger release or open trigger finger release (conventional method). [name] is the only surgeon within the Mass General Brigham (MGB) hospitals that performs ultrasound-guided trigger finger release. All other surgeons perform open trigger finger releases.

Surgeons will measure range of motion and grip strength preoperatively and during postoperative visits, which is part of routine care. We will also administer questionnaires to see how patients are doing postoperatively. See the '6. Study Procedures' for a more elaborate description of the visits.

4. Subject Selection

Inclusion criteria:

1. ≥ 18 years of age
2. Clinical diagnosis of trigger finger
3. Patient has failed conservative treatment or elects not to undergo conservative treatment
4. Surgeon agrees that surgery is indicated
5. Subject agrees to complete follow-up questionnaires over a 6-month period

Exclusion criteria:

1. Prior surgery on the target finger
2. History of prior surgical pulley release in the target hand
3. History of prior surgical pulley release in the contralateral hand within 3 months of enrollment or with persistent symptoms that interfere with normal daily activities or work at the time of consent
4. Corticosteroid injection in the target finger or hand within 6 weeks of surgery
5. Presence of additional process in the target wrist or hand requiring additional intervention beyond pulley release (e.g., neurolysis, mass removal, tenosynovectomy)
6. Clinically significant trauma or deformity of the upper limb (shoulder to hand) on the target side
7. Clinically significant vascular disease (including Raynaud's phenomenon) of the upper limb (shoulder to hand) on the target side
8. Clinically significant neurological disorder (including complex regional pain syndrome) of the upper limb (shoulder to hand) on the target side
9. Planned surgical or interventional procedure on the contralateral wrist or hand

10. Systemic inflammatory disease (e.g., rheumatoid arthritis, lupus)
11. Amyloidosis
12. Diabetes not controlled by a stable dose of medication over the past three months
13. Pregnant or planning pregnancy in the next 6 months
14. Workers' compensation subjects

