We will include all patients who meet the inclusion criteria. We do not exclude patients based on race, color, national origin, sex, sexual orientation, or religion. We will not enroll vulnerable patient populations in this study.

5. Subject Enrollment

Patients will be prescreened through retrospective manual chart review.

Patients will be contacted in person at one of the MGB hospitals (MGH main campus, MGH Waltham, MGH Danvers, BWH main campus, BWH Faulkner, and BWH Foxborough). Patients who meet the inclusion criteria will get a summary of the study by an orthopedic surgeon or a study staff member to see if they are interested. If patients are interested, they will receive the study fact sheet, and the surgeon or study staff member will explain the study in more detail and answer any questions the patient may have. Subjects will be asked to complete the questionnaire either in person or over email or telephone before surgery. Subjects who opt to not complete the questionnaire in person will be contacted using the email or telephone script approved in this study. Subjects who do not complete the pre-op questionnaire before surgery will be withdrawn. Subjects can opt to receive an encrypted or unencrypted email. Subjects who indicate verbally in the outpatient clinic that they do not wish to participate will not be included in the study.

Depending on the treating surgeon, patients will either be treated with an open trigger finger release or an ultrasound-guided trigger finger release.

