6. STUDY PROCEDURES

Study visits

Visits	Procedures
Visit 1 – before surgery	
- Obtain informed consent- ADL questionnaire (see next section)- Visual analog scale for pain (VAS): pain on a scale of 1 to 10 
The measurements are part of standard care and performed by caregivers
 
- Perform the following measurements: range of motion of the PIP joint of the affected finger (including noting any flexion contracture), distance fingertip to distal palmar crease (DPC), and grip strength using Jamar 2 setting.
Visit/Telephone call 2 (2-4 days after surgery)	
- Take the following questionnaire:
1. Are you able to return to activities of daily living, and what activities do you still have trouble doing? You can list the activities you are having trouble with.2. VAS3. How many oxycodone or other narcotic medications are you taking post-op4. Are you able to return to work?

	
5. Are you satisfied with the procedure, and would you choose to have it again for a similar problem?
 
- Take the ADL questionnaire (see next section)- If in person (part of standard care, only collected by study staff, measurements performed by caregivers): Perform the following measurements: range of motion of the PIP joint of the affected finger (including noting any flexion contracture), distance fingertip to distal palmar crease (DPC), and grip strength using Jamar 2 setting.
Visit/Telephone call 3 (6-8 days after surgery)	
- Take the following questionnaire:
1. Are you able to return to activities of daily living, and what activities do you still have trouble doing? You can list the activities you are having trouble with.2. VAS3. How many oxycodone or other narcotic medications are you taking post-op4. Are you able to return to work?5. Are you satisfied with the procedure, and would you choose to have it again for a similar problem?- Take the ADL questionnaire (see next section)- If in person (part of standard care, only collected by study staff, measurements performed by caregivers): Perform the following measurements: range of motion of the PIP joint of the affected finger (including noting any flexion contracture), distance fingertip to distal palmar crease (DPC), and grip strength using Jamar 2 setting.

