- Range of motion of the PIP joint of the affected finger using a goniometer (in degrees), including any flexion contracture + Distance of fingertip from DPC
- Grip strength in the affected as well as contralateral hand using a dynamometer at Jamar 3 setting (in lbs)
- Return to activities of daily living. One question is: 'What activities can't you do?'. We also take a questionnaire to rate their ability to do certain activities (see questionnaire under this section). Patients can rate their ability to perform each activity on a scale from 1 to 5 (1 indicating no difficulty and 5 indicating unable to perform).
- VAS (a pain scale from 1 – 10, reported by the patient)
- How many oxycodone or other narcotic medications are you taking post-op? The number of pills taken will be given.
- Return to work. Patients give a date of when they started working again. Then we'll calculate the return to work in weeks
- Are you satisfied with the procedure, and would you choose to have it again for a similar problem? Answered with yes or no.
- Complications (i.e., trigger finger recurrence, infection, bleeding, etc.)

ADL questionnaire

Mass General Brigham Institutional Review Board
Intervention/Interaction Detailed Protocol

Opening jar	1	2	3	4	5
Driving	1	2	3	4	5
Household Chores	1	2	3	4	5
Carrying Groceries	1	2	3	4	5
Buttoning	1	2	3	4	5
Bathing	1	2	3	4	5
Cooking	1	2	3	4	5
Writing	1	2	3	4	5
Dressing	1	2	3	4	5
Shopping	1	2	3	4	5
Holding a book	1	2	3	4	5
Eating	1	2	3	4	5
Using a Computer	1	2	3	4	5
Holding a Phone	1	2	3	4	5
Using Toilet	1	2	3	4	5

Description of plans for return of research results as applicable

Not applicable

Definition of primary and secondary outcomes/endpoints

Primary endpoints:

- The 5 questions asked in the section above, together with the *ADL questionnaire*
- Recurrence of trigger finger or incomplete release

Secondary endpoints:

- Range of motion of the PIP joint of the affected finger (including noting any flexion contracture)
- Distance fingertip to distal palmar crease
- Grip strength in the affected hand
- Other complications than recurrence of trigger finger or incomplete release

Local site restrictions or site-specific procedures as applicable

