The visits during the first 3 months are part of standard care. Patients with persistent problems will be seen at the 6-month follow-up as part of standard care. If they are doing well clinically, we will only contact them by phone or email to complete these questionnaires using Redcap (see above for the scheme).

Remuneration as applicable

There is no remuneration for this study.

2. Risks and Discomforts

Trigger finger release is a standard procedure (whether it is open or ultrasound-guided) for a trigger finger.

This study's foreseeable risks and discomforts include the time required to complete the measurements and questionnaires. All electronic information (like measurements in Excel files) will be stored on

password-protected computers in a locked office that only study staff members can access. Study data of the questionnaires will be collected and maintained electronically using REDCap, a secure and HIPAA-compliant web-based application to which only study staff will have access. This limits the risk of a data and confidentiality breach, though it is a possibility.

We do not foresee additional risks for subjects participating in the study. Subjects will receive usual care, regardless of their participation. Physicians will be readily accessible for consultation should a subject experience discomfort while completing the measurements and questionnaires or at any time during the study.

3. Benefits

Patients will not receive any direct benefits from this study. However, their participation will help us to determine clinical outcomes after ultrasound-guided and open trigger finger release, which can help patients and physicians in shared decision-making. Potential benefits of ultrasound-guided trigger finger release could be a faster recovery (faster return to work) and better patient-reported aesthetics.

4. Statistical Analysis

Normally distributed continuous data will be stated as mean \pm standard deviations, non-normally distributed continuous data as medians with interquartile ranges and categorical data as frequencies and percentages.

We plan to statistically compare the postoperative clinical data of open trigger finger release to ultrasound-guided trigger finger release.

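### The between-arm comparison of motion, fingertip distance and grip uses no baseline or contralateral reference, although both are to be collected and the measurer is probably tied to the arm

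*Combined protocol and SAP*

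**What the plan says.** **Who operates.** Section 3 (Prospective part) states that one surgeon "is the only surgeon within the Mass General Brigham (MGB) hospitals that performs ultrasound-guided trigger finger release", and then "All other surgeons perform open trigger finger releases". Section 5 (Subject Enrollment) confirms how patients reach an arm: "Depending on the treating surgeon, patients will either be treated with an open trigger finger release or an ultrasound-guided trigger finger release".

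**Who measures.** Section 3 says "Surgeons will measure range of motion and grip strength preoperatively and during postoperative visits, which is part of routine care". The visit table in section 6 adds fingertip-to-crease distance. For Visit 1 it says "The measurements are part of standard care and performed by caregivers". For later visits it says that caregivers measure, that study staff only collect the values, and that measurement takes place only if the visit is in person.

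**What is collected.** PIP motion, fingertip distance and grip are recorded at Visit 1. The variable list in section 6 includes "Grip strength in the affected as well as contralateral hand using a dynamometer". The secondary endpoint is narrower: "Grip strength in the affected hand". None of the seven visit entries says that both hands are to be tested. The visit entries give Jamar setting 2, and the variable list gives setting 3.

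**How arms are compared.** Statistical Analysis says "We plan to statistically compare the postoperative clinical data of open trigger finger release to ultrasound-guided trigger finger release". The named between-group tests are the unpaired t-test and the Mann-Whitney test. Two time points are used together only in a paired test within one group.

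**The concern.** If each arm is measured mainly by its own clinical team, then goniometer technique, dynamometer and coaching can differ systematically between arms. An unpaired test on postoperative values carries a stable difference of this kind in full and reports it as an effect of technique. Baseline differences enter in the same way, because allocation is not randomised.

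All three functional secondary endpoints are exposed: PIP motion, fingertip distance and grip. Grip in pounds also carries the large between-person variation in strength, part of which the other hand could account for. The preoperative reading and contralateral grip are already listed for collection, but neither has a stated use in the comparison between arms.

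**Working it through.** **1. The plan's own figure.** Power analysis states d = 0.5, alpha 0.05, power 0.80, and 51 per group. With a one-sided t-test the noncentrality is 0.5 × √(51/2) = 2.525 and the power is 0.806. At 50 per group it is 0.799, so 51 is reproduced. Two-sided, 51 per group gives 70.6%. The plan does not state sidedness. That is a separate matter; two-sided 0.05 is assumed below.

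**2. A constant measurer offset, analysed on postoperative values.** Assume no true difference and an offset of b standard deviations between arms. The noncentrality is b × √(n/2), where √(51/2) = 5.050 and √(30/2) = 3.873. Critical values are 1.984 (100 df) and 2.002 (58 df). The 30 per arm is an assumption, shown because measurement is in person only.

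| Offset b (assumed) | Noncentrality, n = 51 | Declared significant | Noncentrality, n = 30 | Declared significant |
|---|---|---|---|---|
| 0.2 | 1.010 | 17.0% | 0.775 | 11.9% |
| 0.33 | 1.666 | 37.9% | 1.278 | 24.2% |
| 0.5 | 2.525 | 70.6% | 1.936 | 47.8% |

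**3. The same offset with the baseline used.** These results come from simulation with 51 per arm, 4,000 runs per setting, the offset equal before and after surgery, and pre-post correlation ρ of 0.3, 0.5 or 0.7.

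- *Change score:* (post + b) − (pre + b) = post − pre, so a stable additive offset cancels. Rejection was 4.8% to 5.2% for b from 0.2 to 0.5.
- *Baseline-adjusted model:* about (1 − ρ) × b remains. At b = 0.3 that is 0.21, 0.15 and 0.09 SD, with rejection of 20.1%, 14.4% and 9.3%, against 32.3% on postoperative values alone. The model shrinks the offset without removing it.
- *Price of the change score:* its variance is 2(1 − ρ) times that of a single reading, so it is noisier when ρ is below 0.5. At ρ = 0.3 and a true difference of 0.5 SD, power is 56% against 70%.
- *A shift that arises only after surgery:* 0.3 SD still gives 24%, 32% and 49% rejection on change scores. The baseline does not help here.

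**4. The other hand, for grip.** Assume that grip in the two hands correlates at r with equal SDs. The detectable difference scales with the square root of the variance left.

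| r (assumed) | Difference between hands: 2(1 − r) | Shrinkage | Covariate: 1 − r² | Shrinkage |
|---|---|---|---|---|
| 0.7 | 0.60 | 23% | 0.51 | 29% |
| 0.8 | 0.40 | 37% | 0.36 | 40% |
| 0.9 | 0.20 | 55% | 0.19 | 56% |

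At r = 0.5 the difference between hands gains nothing, since 2(1 − 0.5) = 1. A ratio does not cancel an additive offset, because (A + b)/(C + b) is not A/C.

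**The case against.** - **The tie between measurer and arm is an inference.** A reader might conclude that each arm is certainly measured by its own surgical team. The documents do not go that far. Section 3 says surgeons, the more detailed visit table says caregivers, and staff shared between arms are not ruled out. What stands is that no shared or blinded assessor and no common training is described, while treatment follows the surgeon.
- **The plan does not choose against baseline.** A reader might infer that change scores are excluded. They are not: an unpaired t-test could be run on them. But none is specified between arms, and postoperative values are the plain reading.
- **The sizes are illustrative.** No measurer difference is documented, and fewer than 51 per arm may be measured. At six months, only patients with persistent problems are seen in person as standard care. Several open-arm measurers would also partly average out, but the single-surgeon arm limits this. With random measurer effects (assumed intraclass correlation 0.01 to 0.10, and 3 to 10 open surgeons), type I error is still about 8% to 34%.
- **The references are imperfect.** Change scores are open to regression to the mean if baselines differ. The contralateral hand is not fully screened: the trauma, vascular and neurological exclusions apply to the target side, and an earlier contralateral release can be allowed.
- **The fix does not make the comparison unconfounded.** Unblinded postoperative drift and surgeon skill stay bound to technique. This limits the remedy, but it is no defence of unreferenced postoperative values, which share both weaknesses.

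**Conclusion.** The point holds as a cheap improvement to the secondary analyses. The named comparison between arms leaves stable measurer offsets and baseline differences in the result, although references that would cancel or reduce them are already to be collected. Under an assumed constant offset of 0.2 to 0.5 SD, false-positive rates are 17% to 71% with 51 measured per arm and 12% to 48% with 30. They are about 5% on change from baseline.

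That contrast requires the same team to measure before and after surgery with the same additive error. The grip gain of 23% to 56% rests on an assumed between-hand correlation of 0.7 to 0.9. The documents do not support saying that such an offset exists, or that any particular result would be false. The primary questionnaire endpoints, which the power analysis covers, are not affected by this point.

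**What to change.** 1. For PIP motion, fingertip distance and grip, pre-specify a between-arm comparison of change from the preoperative value, reported together with a baseline-adjusted model. State that the first cancels a stable additive offset and the second only shrinks it. Keep uncorrected postoperative values as supportive.
2. For grip, also report the affected-minus-contralateral difference at the same visit, or use contralateral grip as a covariate. A ratio should not lead.
3. Add both hands to the seven visit entries so that they match the variable list, and reconcile Jamar setting 2 in the visit table with setting 3 in that list. Teams following different passages would themselves create a measuring difference.
4. State who measures in each arm, since section 3 and the visit table use different terms.
5. Record the limits in the plan: noise in change scores when the pre-post correlation is below 0.5, regression to the mean, the partly unscreened contralateral hand, and the remaining confounding with drift and surgeon skill.

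The cost is a few sentences of analysis text and small edits to the visit table. No new patients, visits or listed variables are needed.

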15. Inability to provide a legally acceptable Informed Consent Form and/or comply with all follow-up requirements, including patients who do not speak English
16. Subject has other medical, social, or psychological conditions that, in the opinion of the investigator, preclude them from receiving the pre-treatment, required treatment, and post-treatment procedures and evaluations.
17. Trigger Thumb

How individuals are identified for recruitment, including description of the use of recruitment materials such as flyers, brochures, advertisements, letters, etc.

We are selecting patients interested in undergoing surgical treatment for a trigger finger. Thus, these patients are being seen by a hand surgeon at one of the hospitals within the MGB system (MGH main campus, MGH MGH Waltham, MGH Danvers, BWH main campus, BWH Faulkner and BWH Foxborough) for a trigger finger.

Who is responsible (role on research team) for identifying and recruiting individuals

The orthopedic surgeons and study staff at one of the MGB hospitals (MGH main campus, MGH MGH Waltham, MGH Danvers, BWH main campus, BWH Faulkner, and BWH Foxborough).

When individuals are recruited

Individuals are recruited when indicated for trigger finger release at the outpatient clinic if eligible.

Where individuals are recruited

Patients are recruited at the outpatient clinic of one of the MGB hospitals (MGH main campus, MGH MGH Waltham, MGH Danvers, BWH main campus, BWH Faulkner, and BWH Foxborough).

How recruitment goals match the prevalence rates of the condition/disease being studied and the populations most impacted by the condition/disease being studied

Trigger finger release is a very common procedure to relieve symptoms of a trigger finger. Many patients get treatment for this disease within the MGB hospitals (MGH main campus, MGH MGH Waltham, MGH Danvers, BWH main campus, BWH Faulkner, and BWH Foxborough). The prevalence is higher in diabetic patients than in the general population (10, 11). The recruitment goals will match the prevalence rates of the condition as it is a very common disease, and many patients with comorbidities (i.e., diabetes, thyroid disease) receive treatment within the MGB hospitals (MGH main campus, MGH MGH Waltham, MGH Danvers, BWH main campus, BWH Faulkner and BWH Foxborough).

Methods to enhance enrollment of diverse individuals and under-represented populations

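### No criterion limits how many fingers of the target hand are released, so digit count could be read as a technique effect on patient- and hand-level outcomes

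*Combined protocol and SAP*

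**What the plan says.** All references are to the combined protocol and SAP.

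- **Eligibility (section 4).** The diagnostic inclusion criterion is "Clinical diagnosis of trigger finger", with no number of digits. Exclusion 2 is "History of prior surgical pulley release in the target hand". Exclusion 5 is "Presence of additional process in the target wrist or hand requiring additional intervention beyond pulley release", with neurolysis, mass removal and tenosynovectomy as its examples. Exclusion 9 is "Planned surgical or interventional procedure on the contralateral wrist or hand". Exclusion 17 is "Trigger Thumb", without qualification.
- **Allocation (section 5).** "Depending on the treating surgeon, patients will either be treated with an open trigger finger release or an ultrasound-guided trigger finger release". Section 3 adds that a single surgeon performs all the ultrasound-guided releases in the hospital system.
- **Outcomes (section 6).** The primary endpoints are the five questions (return to daily activities, VAS pain, narcotic pills, return to work, satisfaction) with the 15-item ADL questionnaire, and recurrence or incomplete release. Secondary endpoints include "Grip strength in the affected hand", PIP range of motion and the distance from fingertip to palmar crease.
- **Baseline data (section 3).** "Patient characteristics and disease-related (trigger finger) variables will be collected retrospectively from patient charts on EPIC". Number of digits is not named there or in the variable list in section 6.
- **Analysis (Statistical Analysis).** Arms are compared by unpaired t-test, Mann-Whitney, Fisher's exact or chi-squared test, with no covariates. The power analysis uses an effect size of 0.5, alpha 0.05 and power 0.80, giving 51 per group (53 if non-normal).

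**The concern.** The criteria treat other hand surgery as interference. Any earlier pulley release in the target hand excludes a patient, and so does a planned procedure on the opposite hand. A simultaneous or planned staged release of another finger in the hand being scored does not.

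Most of the primary outcomes cannot be assigned to one finger. Opening a jar, buttoning, pills taken and return to work are answered for the patient as a whole, and grip is measured for the whole hand. A patient with two fingers released contributes the burden of both under one target finger.

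This would matter less under randomisation, which would tend to balance digit count. Here arm is decided by who operates. Any difference between the ultrasound-guided surgeon and the others in how often several fingers are treated together, or in who is referred, goes straight into an unadjusted comparison. A staged second release would also disturb pain and function partway through the six months.

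**Working it through.** **1. Is a second finger release barred?** Taking the criteria in turn:

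| Criterion | What it reaches | Concurrent release, another finger, same hand | Planned later release, another finger, same hand |
|---|---|---|---|
| Exclusion 2 | Prior pulley release, target hand | No | No |
| Exclusion 5 | Same-hand intervention other than pulley release | No | No |
| Exclusion 9 | Planned procedure, opposite side | No | No |
| Exclusion 17 | Trigger thumb | Thumb only | Thumb only |

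Nothing bars it for the fingers. The thumb is removed.

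**2. The plan's own sample size.** A one-sided two-sample t-test with d = 0.5, alpha 0.05 and power 0.80 needs n = 50.15, so 51 per arm and 102 in total. Dividing by the Mann-Whitney efficiency, 50.15 / (3/π) = 52.5, so 53 per arm and 106. Both match the plan. The two-sided t-test would need 64 per arm (128). The plan does not state sidedness, so both are carried below. The digit-count point does not depend on these totals. They supply only the 0.5 SD yardstick and the 51 per arm.

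**3. Size of the possible bias.** Formula: bias = (difference between arms in multi-digit share) × (effect of multi-digit release on the score, in SD). Neither input is in the documents. Both are assumptions: a difference of 10 to 20 percentage points (for example 5% vs 15%, or 5% vs 25%) and an effect of 0.3 to 0.8 SD.

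With 51 per arm, the standard error of the difference is √(2/51) = 0.198 SD. The false-positive rate when technique has no effect follows by shifting the test statistic by bias / 0.198. The one-sided column assumes the bias lies in the tested direction.

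| Share difference | Effect (SD) | Bias (SD) | Share of 0.5 SD | Two-sided error | One-sided error |
|---|---|---|---|---|---|
| 0 | any | 0 | 0% | 5.0% | 5.0% |
| 0.10 | 0.3 | 0.03 | 6% | 5.3% | 6.8% |
| 0.10 | 0.8 | 0.08 | 16% | 6.9% | 10.7% |
| 0.20 | 0.3 | 0.06 | 12% | 6.1% | 9.0% |
| 0.20 | 0.8 | 0.16 | 32% | 12.7% | 20.1% |

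**4. Equal shares.** If the same proportion p of each arm is multi-digit, the variance rises to 1 + p(1 − p) × effect². For p = 0.10 and effect 0.3 this is 1.008, and one-sided power is 80.3%. For p = 0.30 and effect 0.8 it is 1.134, and power is 76.1%, against 80.6% with no multi-digit patients. There is no bias.

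**5. Cost of analysing single-digit patients only.** With assumed shares of 5% and 25%, 51 × 0.95 ≈ 48 and 51 × 0.75 ≈ 38 remain. Power at d = 0.5 falls from 80.6% to about 74% one-sided, or from 70.6% to about 62% two-sided.

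**The case against.** The strongest reply is that eligibility is inferred from silence. The protocol speaks throughout of one target or affected finger and describes release of one A1 pulley. A second triggering finger might also be called an additional process in the hand under exclusion 5. This stands in part: single-digit cases may well have been intended. But exclusion 5 turns on whether the extra intervention goes beyond pulley release, its examples are all of another kind, and no rule enforces one finger or says how a target is chosen among several.

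Second, a reader might infer that a thumb released alongside fingers is also admitted. The text does not support that. Exclusion 17 is unqualified, whereas other criteria specify the target finger or hand when they mean it.

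Third, a reader might infer that the comparison is already contaminated. The documents do not show this. They give no multi-digit rate, no difference between arms and no effect of an extra release, and equal shares produce no bias.

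Fourth, it is tempting to say that covariate adjustment cannot help because the burden arises after baseline. That is true of adjusting for preoperative scores, and of later surgery. It is not true of the number of digits planned for release, which is normally known before the operation and can serve as a covariate or stratum.

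Finally, recurrence, PIP motion and fingertip distance are largely finger-specific and little affected, the documents do not say which site the VAS rates, and digit count is only one of several possible confounders when arm follows surgeon. All of this stands and limits the scope. It does not remove the gap, which is specific and can be closed on its own.

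**Conclusion.** The point holds as a gap in the eligibility rules and the analysis plan. Concurrent or planned staged release of another finger of the target hand is not barred, digit count is not a named variable, and nothing in the unadjusted, surgeon-determined comparison would prevent or correct an imbalance.

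The consequence is a credible risk, not a demonstrated bias. Under the assumed inputs it runs from 0.03 to 0.16 SD. That is not enough alone to produce the planned 0.5 SD difference, but at the upper end it would raise a nominal 5% two-sided error to about 13%. If shares are equal, the only cost is a few points of power. The point concerns the patient- and hand-level outcomes. It should be corrected, because the criteria already guard against interference from the other hand and leave the measured hand open.

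**What to change.** 1. **Eligibility.** Extend exclusion 9 to planned release of any other digit of the target hand, at the index operation or during the six-month follow-up.
2. **Patients already enrolled.** Extract the number of digits released from the chart, which is already a data source. Adjust or stratify the between-arm comparison of patient- and hand-level outcomes for it. Report the single-digit comparison as a sensitivity analysis.
3. **Later hand procedures.** Record the date of any such procedure and report results with and without scores after that date.

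The cost is one eligibility line, one chart field, one covariate or stratum, and a date. Some recruits are lost, though the protocol describes the procedure as very common, and results will apply to single-finger release. The restricted analysis has less power: about 74% one-sided with 48 vs 38 patients in the assumed example. That is why it is proposed as a sensitivity analysis and not as the main comparison.
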